### 3.3.4 Visits 4, 6, 7, 9, 10, 12-14, 16, 17, 19, 20, 22, 23, 25-27, 29-33, 35-40, 42-46, 48-53, 55-59, 61-66, 68-72, 74-79, 81-85, and 87-92

*Location:* DIAN-TU site or subject's home or other trial-identified location with the trial-designated home health nurse.

*Timing:* Visits as listed below (calculated from day of first dose), with a visit window of +/- 4 days.

Visit No.	4	6	7	9	10	12	13	14	16	17	19	20
Week	8	16	20	28	32	40	44	48	56	60	68	72

Visit No.	22	23	25	26	27	29	30	31	32	33	35	36
Week	80	84	92	96	100	108	112	116	120	124	132	136

Visit No.	37	38	39	40	42	43	44	45	46	48	49	50
Week	140	144	148	152	160	164	168	172	176	184	188	192

Visit No.	51	52	53	55	56	57	58	59	61	62	63	64
Week	196	200	204	212	216	220	224	228	236	240	244	248

Visit No.	65	66	68	69	70	71	72	74	75	76	77	78
Week	252	256	264	268	272	276	280	288	292	296	300	304

Visit No.	79	81	82	83	84	85	87	88	89	90	91	92
Week	308	316	320	324	328	332	340	344	348	352	356	360

*Procedures:*

- Concomitant medication review
- Adverse event assessment
- Vital signs (blood pressure, heart rate, respiratory rate, and body temperature; weight may be obtained approximately every 3 months per section 6.1.6 of main protocol)
- Urine pregnancy testing for women of childbearing potential
- Study drug dosing as specified in section 2.1.5
- Phone call (required after Visit 4; not required at all other home/off-site visits but direct site-subject contact should occur at least once every 3 months throughout the study): the DIAN-TU site coordinator calls subject and addresses any concerns, discusses scheduling of safety MRI and next visits, and encourages compliance

**3.3.5 Visits 5, 11, 18, and 24**

*Location:* DIAN-TU site or subject's home or other trial-identified location with the trial-designated home health nurse.

*Timing:* Visits as listed below (calculated from day of first dose), with a visit window of +/- 4 days.

Visit No.	5	11	18	24
Week	12	36	64	88

*Procedures:*

- Concomitant medication review
- Adverse event assessment
- Vital signs (blood pressure, heart rate, respiratory rate, and body temperature; weight may be obtained approximately every 3 months per section 6.1.6 of main protocol)
- C-SSRS administration
- Urine pregnancy testing for women of childbearing potential
- Study drug dosing and post-dose monitoring/evaluation as specified in section 2.1.5
- Phone call (required after Visit 5; not required at all other home/off-site visits but direct site-subject contact should occur at least once every 3 months throughout the study): the DIAN-TU site coordinator calls subject and addresses any concerns, discusses scheduling of safety MRI and next visits, and encourages compliance

### 3.3.6 Visit 8

*Location:* DIAN-TU site or subject's home or other trial-identified location with the trial-designated home health nurse.

*Timing:* 24 weeks +/- 4 days from Visit 2 (calculated from day of first dose)

*Procedures:*

- Cognitive battery subset (per section 6.1.14 of main protocol)
- Concomitant medication review
- Adverse event assessment
- Vital signs (blood pressure, heart rate, respiratory rate, and body temperature; weight may be obtained approximately every 3 months per section 6.1.6 of main protocol)
- 12-lead ECG
- C-SSRS administration
- Blood draw for:
  - Clinical laboratory tests
  - [REDACTED]
- Urine pregnancy testing for women of childbearing potential
- Study drug dosing and post-dose monitoring/evaluation as specified in section 2.1.5
- Phone call (not required at all home/off-site visits but direct site-subject contact should occur at least once every 3 months throughout the study): the DIAN-TU site coordinator

calls subject and addresses any concerns, discusses scheduling of safety MRI and next visits, and encourages compliance

### 3.3.7 VISIT 15: ANNUAL VISIT AT HOST DIAN-TU SITE

*Location:* Host DIAN-TU site

*Timing:* 52 weeks +/- 7 days from Visit 2 (calculated from day of first dose); approximately a 3-4 day visit. The sequence and timing of visit procedures is very important. Requirements and suggested timing of study procedures are detailed in the *Global Manual of Operations*. For subjects who live near the study site, these visit procedures may be scheduled over a longer time period of up to 2 weeks.

*Procedures:*

- Concomitant Medications
  - Adverse Event Assessment
  - Vital signs (blood pressure, heart rate, respiratory rate, body temperature, weight and height)
  - 12-lead ECG
  - Administration of C-SSRS
  - Blood draw for:
    - Clinical laboratory tests (hematology, chemistry, urinalysis)
    - [REDACTED]
  - Urine pregnancy testing for women of childbearing potential
  - Physical and neurological examination
  - Clinical assessments:
    - Clinical Dementia Rating (CDR) including calculation of Clinical Dementia Rating Sum of Boxes (CDR-SB)
    - [REDACTED]
    - Functional Assessment Scale (FAS)
    - [REDACTED]
- NOTE: For each subject, the CDR and assessment of clinical diagnosis should be administered by the same experienced clinician at all visits. Whenever possible the CDR rater should not be involved in other clinical assessments (e.g., MMSE, FAS, GDS, NPI-Q) or in cognitive testing.
- Complete cognitive battery (per section 6.1.14 of main protocol)
  - Annual MRI (including structural and functional MRI) uploaded immediately to ensure reading obtained prior to dosing. This MRI includes safety MRI sequences. MRI should be performed before lumbar puncture, if on the same date

- [REDACTED]
- PET imaging:
  - [C]PiB-PET
  - [REDACTED]
- Study drug dosing and post-dose monitoring/evaluation as specified in section 2.1.5
- Follow-up phone call or brief visit within 24 hours after LP, and no longer than 48 hours later, to review any adverse events

### 3.3.8 Visit 21

*Location:* DIAN-TU site or subject's home or other trial-identified location with the trial-designated home health nurse.

*Timing* 76 weeks +/- 4 days from Visit 2 (calculated from day of first dose)

*Procedures:*

- Cognitive battery subset (per section 6.1.14 of main protocol)
- Concomitant medication review
- Adverse event assessment
- Vital signs (blood pressure, heart rate, respiratory rate, and body temperature; weight may be obtained approximately every 3 months per section 6.1.6 of main protocol)
- 12-lead ECG
- C-SSRS administration
- Clinical laboratory tests (hematology, chemistry, urinalysis)
- Urine pregnancy testing for women of childbearing potential
- Study drug dosing and post-dose monitoring/evaluation as specified in section 2.1.5
- Phone call (not required at all home/off-site visits but direct site-subject contact should occur at least once every 3 months throughout the study): the DIAN-TU site coordinator calls subject and addresses any concerns, discusses scheduling of safety MRI and next visits, and encourages compliance

### 3.3.9 VISIT 28: ANNUAL VISIT AT HOST DIAN-TU SITE

*Location:* Host DIAN-TU site

*Timing:* 104 weeks +/- 7 days from Visit 2 (calculated from day of first dose); approximately a 3-4 day visit. The sequence and timing of visit procedures is very important. Requirements and suggested timing of study procedures are detailed in the *Global Manual of Operations*. For subjects who live near the study site, these visit procedures may be scheduled over a longer time period of up to 2 weeks.

*Procedures:*

- Concomitant Medications
  - Adverse Event Assessment
  - Vital signs (blood pressure, heart rate, respiratory rate, body temperature, weight and height)
  - 12-lead ECG
  - Administration of C-SSRS
  - Blood draw for:
    - Clinical laboratory tests (hematology, chemistry, urinalysis)  
█ [REDACTED]
  - Urine pregnancy testing for women of childbearing potential
  - Physical and neurological examination
  - Clinical assessments:
    - Clinical Dementia Rating (CDR) including calculation of Clinical Dementia Rating Sum of Boxes (CDR-SB)  
█ [REDACTED]
    - Assessment of clinical diagnosis and clinician judgment of symptoms  
█ [REDACTED]
    - Functional Assessment Scale (FAS)  
█ [REDACTED]
- OTE: For each subject, the CDR and assessment of clinical diagnosis should be administered by the same experienced clinician at all visits. Whenever possible the CDR rater should not be involved in other clinical assessments (e.g., MMSE, FAS, GDS, NPI-Q) or in cognitive testing.
- Complete cognitive battery (per section 6.1.14 of main protocol)
  - Annual MRI (including structural and functional MRI) uploaded immediately to ensure reading obtained prior to dosing. This MRI includes safety MRI sequences. MRI should be performed before lumbar puncture, if on the same date  
█ [REDACTED]
  - PET imaging:
    - [C]PiB-PET  
█ [REDACTED]
  - Study drug dosing and post-dose monitoring/evaluation as specified in section 2.1.5
  - Follow-up phone call or brief visit within 24 hours after LP, and no longer than 48 hours later, to review any adverse events

### 3.3.10 Visits 34 and 47

*Location:* DIAN-TU site or subject's home or other trial-identified location with the trial-designated home health nurse.

*Timing:* 128 and 180 weeks +/- 4 days from Visit 2 (calculated from day of first dose).

*Procedures:*

- Cognitive battery subset (per section 6.1.14 of main protocol)
- Concomitant medication review
- Adverse event assessment
- Vital signs (blood pressure, heart rate, respiratory rate, and body temperature; weight may be obtained approximately every 3 months per section 6.1.6 of main protocol)
- 12-lead ECG
- C-SSRS administration
- Clinical laboratory tests (hematology, chemistry, urinalysis)
- Urine pregnancy testing for women of childbearing potential
- Study drug dosing and post-dose monitoring/evaluation as specified in section 2.1.5
- Phone call (not required at all home/off-site visits but direct site-subject contact should occur at least once every 3 months throughout the study): the DIAN-TU site coordinator calls subject and addresses any concerns, discusses scheduling of next visits, and encourages compliance

### 3.3.11 VISIT 41: ANNUAL VISIT AT HOST DIAN-TU SITE

*Location:* Host DIAN-TU site

*Timing:* 156 weeks +/- 7 days from Visit 2 (calculated from day of first dose); approximately a 2-3 day visit. The sequence and timing of visit procedures is very important. Requirements and suggested timing of events are detailed in the *Global Manual of Operations*. For subjects who live near the study site, these visit procedures may be scheduled over a longer time period of up to 2 weeks.

*Procedures:*

- Concomitant Medications
- Adverse Event Assessment
- Vital signs (blood pressure, heart rate, respiratory rate, body temperature, weight and height)
- 12-lead ECG
- Administration of C-SSRS
- Clinical laboratory tests
- Urine pregnancy testing for women of childbearing potential
- Physical and neurological examination

- Clinical assessments:
  - Clinical Dementia Rating (CDR) including calculation of Clinical Dementia Rating Sum of Boxes (CDR-SB)
  - Assessment of clinical diagnosis and clinician judgment of symptoms

█ [REDACTED]

- Functional Assessment Scale (FAS)

█ [REDACTED]

OTE: For each subject, the CDR and assessment of clinical diagnosis should be administered by the same experienced clinician at all visits. Whenever possible the CDR rater should not be involved in other clinical assessments (e.g., MMSE, FAS, GDS, NPI-Q) or in cognitive testing

- Complete cognitive battery (per section 6.1.14 of main protocol)
- Annual MRI (including structural and functional MRI) uploaded immediately to ensure reading obtained prior to dosing. This MRI includes safety MRI sequences
- Study drug dosing and post-dose monitoring/evaluation as specified in section 2.1.5

### 3.3.12 VISIT 54: ANNUAL VISIT AT HOST DIAN-TU SITE

*Location:* Host DIAN-TU site

*Timing:* 208 weeks +/- 7 days from Visit 2 (calculated from day of first dose); approximately a 3-4 day visit. The sequence and timing of visit procedures is very important. Requirements and suggested timing of events are detailed in the *Global Manual of Operations*. For subjects who live near the study site, these visit procedures may be scheduled over a longer time period of up to 2 weeks.

*Procedures:*

- Concomitant Medications
  - Adverse Event Assessment
  - Vital signs (blood pressure, heart rate, respiratory rate, body temperature, weight and height)
  - 12-lead ECG
  - Administration of C-SSRS
  - Blood draw for:
    - Clinical laboratory tests (hematology, chemistry, urinalysis)
- █ [REDACTED]
- Serum pregnancy testing for women of childbearing potential, if applicable
- Physical and neurological examination
- Clinical assessments:
  - Clinical Dementia Rating (CDR) including calculation of Clinical Dementia Rating Sum of Boxes (CDR-SB)

- Assessment of clinical diagnosis and clinician judgment of symptoms

- Functional Assessment Scale (FAS)

- Mini-Mental State Exam (MMSE)

NOTE: For each subject, the CDR and assessment of clinical diagnosis should be administered by the same experienced clinician at all visits. Whenever possible the CDR rater should not be involved in other clinical assessments (e.g., MMSE, FAS, GDS, NPI-Q) or in cognitive testing.

- Complete cognitive battery (per section 6.1.14 of main protocol)
- Annual MRI (including structural and functional MRI) uploaded immediately to ensure reading obtained prior to dosing. This MRI includes safety MRI sequences. MRI should be performed before lumbar puncture, if on the same date

- PET imaging:

- [C]PiB-PET

- FDG-PET (subject should be fasting for 4 hours prior to FDG-PET)

- Study drug dosing and post-dose monitoring/evaluation as specified in section 2.1.5
- Follow-up phone call or brief visit within 24 hours after LP, and no longer than 48 hours later, to review any adverse events

### 3.3.13 VISITS 60, 73, and 86

*Location:* Host DIAN-TU site

*Timing:* 232, 284, and 336 weeks +/- 7 days from Visit 2 (calculated from day of first dose); approximately a 3-4 day visit.

Visits No.	60	73	86
Week	232	284	336

#### *Procedures:*

- Cognitive battery subset (per section 6.1.14 of main protocol)
- Concomitant Medications
- Adverse Event Assessment
- Vital signs (blood pressure, heart rate, respiratory rate, and body temperature; weight may be obtained approximately every 3 months per section 6.1.6 of main protocol)
- Urine pregnancy testing for women of childbearing potential
- Study drug dosing and post-dose monitoring/evaluation as specified in section 2.1.5

- Phone call (not required at all home/off-site visits but direct site-subject contact should occur at least once every 3 months throughout the study): the DIAN-TU site coordinator calls subject and addresses any concerns, discusses scheduling of safety MRI and next visits, and encourages compliance

### 3.3.14 VISITS 67, 80, and 93: ANNUAL VISITS AT HOST DIAN-TU SITE/END OF DOUBLE-BLIND TREATMENT

*Location:* Host DIAN-TU site

*Timing:* 260, 312, and 364 weeks +/- 7 days from Visit 2 (calculated from day of first dose); approximately a 3-4 day visit. The sequence and timing of visit procedures is very important. Requirements and suggested timing of events are detailed in the *Global Manual of Operations*. For subjects who live near the study site, these visit procedures may be scheduled over a longer time period of up to 2 weeks.

Visits No.	67	80	93
Week	260	312	364

#### *Procedures:*

- Concomitant Medications
  - Adverse Event Assessment
  - Vital signs (blood pressure, heart rate, respiratory rate, and body temperature; weight may be obtained approximately every 3 months per section 6.1.6 of main protocol)
  - 12-lead ECG
  - Administration of C-SSRS
  - Clinical laboratory tests (hematology, chemistry, urinalysis)
  - Urine pregnancy testing for women of childbearing potential at Visits 67 and 80; serum pregnancy testing at Visit 93
  - Physical and neurological examination
  - Clinical assessments:
    - Clinical Dementia Rating (CDR) including calculation of Clinical Dementia Rating Sum of Boxes (CDR-SB)
    - Assessment of clinical diagnosis and clinician judgment of symptoms
    - Functional Assessment Scale (FAS)
- OTE: For each subject, the CDR and assessment of clinical diagnosis should be administered by the same experienced clinician at all visits. Whenever possible the CDR rater should not be involved in other clinical assessments (e.g., MMSE, FAS, GDS, NPI-Q) or in cognitive testing.
- Complete cognitive battery (per section 6.1.14 of main protocol)

- Annual MRI (including structural and functional MRI) uploaded immediately to ensure reading obtained prior to dosing. This MRI includes safety MRI sequences
- V67 and V80: Study drug dosing and post-dose monitoring/evaluation as specified in section 2.1.5. Note: dose will not be administered at Visit 93

### 3.3.15 End of Study Visit

*Location:* DIAN-TU site or subject's home or other trial-identified location with the trial-designated home health nurse.

*Timing:* The end of study safety follow-up visit should be performed 12 weeks (+/- 7 days) after the last dose of double-blind treatment.

*Procedures:*

- Concomitant Medications
- Adverse Event Assessment
- Vital signs (blood pressure, heart rate, respiratory rate, and body temperature; weight may be obtained approximately every 3 months per section 6.1.6 of main protocol)
- Clinical laboratory tests
- Serum pregnancy testing for women of childbearing potential

### 3.3.16 Early Termination/Post-treatment Follow-up

If a subject withdraws, is terminated from the study prior to completion, or is in a study drug arm that is stopped prior to the end of the double-blind treatment period, every effort should be made to schedule an early termination visit that will include all procedures done at Visit 54 for those not yet having completed that visit, or Visit 93 for those beyond V54. Drug-specific testing should also be obtained at early termination visit only if prior to completion of V54, week 208 (see section 1.12). PET imaging studies may be omitted if early termination occurs less than 6 months after the previous PET imaging or if precluded by local regulations/dosimetry limits. Other procedures may also be eliminated on a case-by-case basis, as determined by the sponsor.

Per the main protocol section 6.3.7, any subject meeting study drug discontinuation criteria per main protocol section 4.4.1 due to safety reasons, inability to continue treatment administration/dosing, or perform study procedures, will be encouraged to continue participation in any of the scheduled clinical, cognitive, and/or biomarker assessments that they are able to perform, even though dosing has concluded. The determination of which assessments are to be attempted/completed will be decided by the site principal investigator and sponsor and will be based on the subject's capabilities, the benefit to the study, and the risk associated with continued participation at the time of study drug discontinuation. The level of continued participation may change if/as the subject's status changes.

### 3.3.17 Safety Magnetic Resonance Imaging

Safety MRI visits will be scheduled over the entire course of the study.

*Location:* Safety MRIs may be done at the host DIAN-TU site or, for subjects who live at a distance from the host DIAN-TU site, safety MRIs may be performed at an ADNI/ADCS site if possible or at a 3T scanner near the subject's home.

*Timing:* See section 1.13.1. Sites must ensure that study visits are scheduled so that MRIs are uploaded and available for central read at least 10 working days before next administration of study drug for parenterally administered drugs.

*Procedures:* Safety MRIs on 3T scanners will be done primarily to monitor for ARIA. See section 1.13.1 and section 6.1.16 of the main protocol for more information. Detailed requirements are provided in the *MRI Technical Manual*.

### 3.4 [REDACTED]

[REDACTED]

[REDACTED]

[REDACTED]

[REDACTED]

[REDACTED]

[REDACTED]

[REDACTED]

[REDACTED]

[REDACTED]

[REDACTED]

[REDACTED]

---

[REDACTED]

[REDACTED]

[REDACTED]

[REDACTED]

[REDACTED]

[REDACTED]

[REDACTED]

[REDACTED]

[REDACTED]

- Clinical assessments:

[REDACTED]

[REDACTED]

- [REDACTED]

[REDACTED]

[REDACTED]	[REDACTED]	[REDACTED]	[REDACTED]	[REDACTED]	[REDACTED]	[REDACTED]	[REDACTED]	[REDACTED]	[REDACTED]	[REDACTED]	[REDACTED]
[REDACTED]	[REDACTED]	[REDACTED]	[REDACTED]	[REDACTED]	[REDACTED]	[REDACTED]	[REDACTED]	[REDACTED]	[REDACTED]	[REDACTED]	[REDACTED]

[REDACTED]	[REDACTED]	[REDACTED]	[REDACTED]	[REDACTED]	[REDACTED]	[REDACTED]	[REDACTED]	[REDACTED]	[REDACTED]	[REDACTED]
[REDACTED]	[REDACTED]	[REDACTED]	[REDACTED]	[REDACTED]	[REDACTED]	[REDACTED]	[REDACTED]	[REDACTED]	[REDACTED]	[REDACTED]

[REDACTED]

[REDACTED]

[REDACTED]

[Redacted text block]

[Redacted text block]

[Redacted text block]

[Redacted text block]

rater should not be involved in other clinical assessments (e.g., MMSE, FAS, GDS, NPI-Q)

[REDACTED]

[REDACTED]

[REDACTED]

[REDACTED]

[REDACTED]

[REDACTED]

[REDACTED]

[REDACTED]

[REDACTED]

[REDACTED]

[REDACTED]

[REDACTED]

[REDACTED]

[REDACTED]

[REDACTED]

- [REDACTED]

[REDACTED]

[REDACTED]

[REDACTED]

[REDACTED]

[REDACTED]

[REDACTED]

## **4 DRUG-SPECIFIC ANALYSIS PLAN**

### **4.1 DIAN-Multivariate Cognitive Endpoint Power Analysis and Sample Size Determination**

The power was estimated based on the multivariate disease progression model (MDPM) and the DIAN-MCE primary endpoint with four arms: the gantenerumab active drug arm, the solanezumab active drug arm, the mutation positive placebos, and the eligible DIAN-OBS subjects. For details, refer to the SAP and gantenerumab-specific SAP appendix.

### **4.2 Biomarker Endpoint Statistical Analysis, Power and Sample Size Justification**

#### **4.2.1 Biomarker Endpoint Power Analysis**

Power analysis for the biomarker endpoints suggests 42 mutation positive subjects in the gantenerumab arm along with 27 mutation carriers in the pooled placebo group will provide

over 99% power to detect the projected effect size for changes in [C]PiB-PET. Recruitment goal is for 69 mutation positive subjects; 52 on gantenerumab and 17 on placebo, for a total of 34 in the pooled placebo group. These recruitment goals will allow for 5% annual attrition rate.

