	
interim analysis is significant, the study drug may be terminated earlier for efficacy. Details about any planned interim analyses are described in each drug-specific appendix.
 
All interim analyses will be conducted on the modified intent-to-treat (mITT) population, which is defined as all subjects who will be randomized, treated, and assessed for their primary cognitive outcomes at least once after the baseline assessment.
 
Efficacy analyses for the cognitive endpoint: All efficacy analyses will be conducted on the modified intent-to-treat (mITT) population. The primary efficacy hypothesis will be tested by comparing the cognitive decline relative to estimated years from symptom onset (EYO) between the active drug, the mutation positive placebos, and the eligible DIAN-OBS subjects using the cognitive multivariate disease progression model (MDPM) developed by the DIAN-TU. The MDPM includes two subject-level random effects to account for the between-subject variability and a model of the mean rate of decline as a function of EYO. Treatment efficacy will be measured as a proportional slowing in decline of the primary cognitive endpoint in active drug compared with the mutation positive placebos and the eligible DIAN-OBS subjects.

Sample Size Considerations	
For the gantenerumab and solanezumab arms, the recruitment goal was for 52 mutation positive subjects per active drug group and 34 mutation carriers for the mutation positive placebo group to allow for 5% annual attrition during the minimum 4-year double-blind treatment period. Assuming 5% annual attrition rate, at the end of the 4-year study, there will be approximately 42 subjects on each active treatment and 27 mutation positive placebos. Power analysis for the biomarker endpoints suggests that this sample size will provide over 99% power to detect calculated effect sizes for changes in PiB and CSF total A<math>\beta</math> 1-42 (A<math>\beta</math>42). Power analysis for the DIAN-MCE suggests that 42 mutation positive subjects in the active drug groups, 27 mutation positive placebos, and eligible DIAN-OBS subjects will provide over 90% power to detect a 40% effect size (slowing of decline in cognition for active drug in comparison to placebo) when the last subject randomized to the study drug arm reaches the end of the minimum 4-year double-blind treatment period.

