#### **4.2.2 Biomarker Endpoint Sample Size Justification**

Table 9 summarizes the power analysis by presenting the estimated SD from the DIAN cohort and the effect size on the annual rate of change for [C]PiB-PET C-SUVR that can be detected by 42 subjects in the active drug group (52 subjects enrolled, assumes 5% annual dropout rate during the trial) and 27 subjects in the pooled placebo group (34 subjects enrolled; assumes a 5% annual dropout) with at least 80% power. For comparison, Table 9 also lists the effect size on the rate of change for the same biomarkers reported by recently published clinical trials. The projected effect size is smaller than all reported effect size for C-SUVR, demonstrating that the proposed sample size provides adequate statistical power to detect reasonable effect sizes. In fact, for the biomarker endpoint used at the interim analysis, the proposed sample size (i.e., 52 in the active drug group and 34 in the pooled placebo group) provides more than 99% statistical power to detect two-thirds of the reported effect size in the literature or through personal communications and at least 80% power even for some other additional endpoints. Also provided are the estimated powers for 12 months of exposure of 675 mg, 900 mg, and 1200 mg (Table 10).

In summary, recruitment of 52 mutation positive subjects to the active drug group (at least 42 completers assuming 5% annual attrition during the study period) and 34 mutation positive subjects to the pooled placebo group (at least 27 completers assuming 5% annual attrition during the study period) would provide statistical power to test the biomarker engagement hypotheses.

**Table 9 The effect size with 80% power in comparison to the reported effect size in a prior study and the corresponding power with proposed sample sizes**

Active Drug	Efficacy outcome	SD for the rate of change/year among untreated carriers (estimated from DIAN data)	Effect size that can be detected with n=42 (active drug) vs. 27 (placebo) completers	Reported effect size (p=p-value, n= sample size of the reported trial)	Estimated power with n=42 (treatment) and n=27 (placebo) for the reported effect size	Estimated power with n=42 (treatment) and n=27 (placebo) to detect 2/3 of the reported effect size	Authors of the reported trials (year)

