Gantenerumab (RO4909832) Stable Dose: 450 	PiB C-SUVR (Primary)	0.137	0.096	0.50 in less than 1 year (n=4 vs. 6 for 200 mg)	>99%	>99%	(Ostrowitzki et al., 2012)

Effect Size = difference between active drug and placebo on the annual rate of change for the corresponding efficacy endpoint that can be detected by 52 subjects in the active drug group (42 after 5% annual attrition) and 34 subjects in the mutation positive (pooled) placebo group (27 after 5% annual attrition)

 Taking a conservative manner, the planned reduction in PiB C-SUVR for dose 450 mg is assumed to be 0.096/year, which is the same as the planned reduction for the current dose 225 mg.

**Table 10 Power to detect the planned differences after dose titration by 52 subjects on active drug (42 after 5% annual attrition) and 34 subjects on placebo (27 after 5% annual attrition)**

Stable Dose	Effect size (SD) that can be detected with n=42 (active drug) vs. 27 (placebo) completers 	Power for 12 months on the stable dose
675 mg	0.144 (0.137)	98.7%
900 mg	0.192 (0.137)	>99%
1200 mg	0.256 (0.137)	>99%

 Assuming that the reduction in PiB C-SUVR for dose 450 mg is 0.096/year, the change/year for dose 675 is 0.144 (= 675/450\*0.096), for dose 900 mg is 0.192 (= 900/450\*0.096), and for 1200 mg is 0.256 (= 1200/450\*0.096). A linear relationship between change/year and dose as well as a consistent standard deviation (SD) is assumed.

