### 4.2 Biomarker Endpoint Statistical Analysis, Power and Sample Size Justification

#### 4.2.1 Biomarker Endpoint Power Analysis

Power analysis for the biomarker endpoints suggests 42 mutation positive subjects in the solanezumab group along with 27 mutation carriers in the pooled placebo group will provide over 99% power to detect the projected effect size for changes in total CSF A $\beta$ 42. Recruitment goal is for 69 mutation positive subjects; 52 on solanezumab and 17 on placebo, for a total of 34 in the pooled placebo group. These recruitment goals will allow for 5% annual attrition rate.

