#### 4.2.2 Biomarker Endpoint Sample Size Justification

Table 8 summarizes the power analysis by presenting the estimated SD from the DIAN cohort and the effect size on the annual rate of change for the CSF biomarker that can be detected by 42 subjects in the active drug group (52 subjects enrolled, assumes 5% annual dropout rate during the trial) and 27 subjects in the pooled placebo group (34 subjects enrolled; assumes a 5% annual dropout) with at least 80% power. For comparison, Table 8 also lists the effect size on the rate of change reported in a prior study. The projected effect size for 400 mg Q4W is conservatively estimated and is smaller than the reported effect size in the prior study. Therefore, the proposed sample size should provide adequate statistical power to detect the projected effect size. For example, for the biomarker endpoint used at the interim analysis, the proposed sample size (i.e., 52 in the active drug group and 34 in the pooled placebo group) provides more than 99% statistical power to detect two-thirds of the reported effect size in the prior study. The projected effect size is expected to be larger after dose escalation to 1600 mg Q4W, thus the proposed sample size will provide more power to detect the treatment effect after dose escalation.

In summary, recruitment of 52 mutation positive subjects to the active drug group (at least 42 completers assuming 5% annual attrition during the study period) and 34 mutation positive subjects to the pooled placebo group (at least 27 completers assuming 5% annual attrition during the study period) would provide adequate statistical power both before and after dose escalation to test the biomarker engagement hypotheses.

**Table 8 The effect size with 80% power in comparison to the reported effect size in a prior study and the corresponding power with the proposed sample size**

Active Drug	Efficacy outcome	SD for the rate of change/year among untreated carriers (estimated from DIAN data)	Effect size that can be detected with n=42 (active drug) vs. 27 (placebo) completers	Reported effect size (p=p-value, n= sample size of the reported trial)	Estimated power with n=42 (treatment) and n=27 (placebo) for the reported effect size	Estimated power with n=42 (treatment) and n=27 (placebo) to detect 2/3 of the reported effect size	Authors of the reported trials (year)

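### The over 99% biomarker power is attached to a projected effect that, at the 225/450 mg planning value, is the 80%-power detectable difference

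*Protocol*

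**What the plan says.** Three places make the claim. Appendix 3, Section 4.2.1 takes "42 mutation positive subjects in the gantenerumab arm along with 27 mutation carriers in the pooled placebo group" and states "over 99% power to detect the projected effect size for changes in" PiB-PET. Appendix 4, Section 4.2.1 states "over 99% power to detect the projected effect size for changes in total CSF" Aβ42 with the same numbers of completers. The synopsis, under Sample Size Considerations, says the sample size "will provide over 99% power to detect calculated effect sizes for changes in PiB and CSF total" Aβ42. None of the three gives a number for the effect.

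Appendix 3, Section 4.2.2 introduces the Table 9 effect as the one that 42 and 27 completers can detect "with at least 80% power". It then argues that the sample size is adequate: "The projected effect size is smaller than all reported effect size for C-SUVR". Table 9 gives an SD of 0.137, a detectable effect of 0.096 per year and a reported effect of 0.50. Its over 99% entries stand in the columns for the reported effect and for two-thirds of it. Footnote 1 adds that "the planned reduction in PiB C-SUVR for dose 450 mg is assumed to be 0.096/year, which is the same as the planned reduction for" the 225 mg dose. Table 10 scales 0.096 by dose, giving 0.144 at 675 mg (98.7%), 0.192 at 900 mg (over 99%) and 0.256 at 1200 mg (over 99%).

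Appendix 4, Section 4.2.2 runs in parallel: "The projected effect size for 400 mg Q4W is conservatively estimated and is smaller than the reported effect size in the prior study". Table 8 gives an SD of 75, a detectable effect of 52.588 pg/mL per year and a reported effect of 170. It too places over 99% against the reported effect and two-thirds of it. The text expects a larger effect after escalation to 1600 mg but does not quantify it.

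**The concern.** In Appendix 3, Section 4.2.2, the projected effect is set against the published one to show that it is modest. The number that the paragraph has just introduced is the 80%-power detectable difference, and footnote 1 then names that same number as the planned reduction at two doses. A planned effect set equal to the 80%-power difference has 80% power by construction. It cannot also have over 99%. The over 99% seems to have moved from the published-effect columns of Tables 8 and 9 to a different effect in the summary sentences.

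Main protocol Section 8.3 makes the biomarker interim a point at which an arm can be adjusted or stopped for futility. A reader who takes the headline at face value will think the design far more sensitive at the planning value than the protocol's own table shows.

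**Working it through.** **Inputs.** Completers 42 and 27 (both Sections 4.2.1). SD 0.137 and effect 0.096 (Table 9). SD 75 and effect 52.588 (Table 8). Planned differences 0.144, 0.192 and 0.256 (Table 10). Reported effects 0.50 and 170. No alpha or sidedness is stated for this test; I assume two-sided 5% and a two-sample t test on 42 + 27 − 2 = 67 degrees of freedom, critical value 1.996.

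**Formula.** SE = SD × √(1/42 + 1/27) = SD × 0.2467. The noncentrality is effect/SE, and power comes from the noncentral t distribution.

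**Reproducing the plan's figures first.**
- Table 8: SE = 75 × 0.2467 = 18.50. The 80%-power difference solves to 52.588, equal to the table to every printed digit. This supports the assumed alpha and test.
- Table 9: SE = 0.137 × 0.2467 = 0.0338. The 80%-power difference solves to 0.0961; the table prints 0.096.
- Table 10 at 675 mg: 0.144/0.0338 = 4.26, power 98.7%, as printed. At 0.192 and 0.256, power exceeds 99.9%.

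**The disputed claim.**

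| Effect | Source | Power, 42 vs 27 |
|---|---|---|
| 0.096/year | planned, 225 and 450 mg | 79.95% |
| 52.588 pg/mL/year | detectable effect, Table 8 | 80.0% |
| 0.144/year | planned, 675 mg | 98.7% |
| 0.192 and 0.256/year | planned, 900 and 1200 mg | over 99.9% |
| 0.333 (0.50 × 2/3) | two-thirds of reported, PiB | over 99.9% |
| 113.3 (170 × 2/3) | two-thirds of reported, CSF | over 99.9% |

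**Can another convention rescue over 99% at 0.096?**
- Normal approximation, 42 vs 27: 81%.
- One-sided 5%, 42 vs 27: 88%.
- Enrolled numbers, 52 vs 34, two-sided: 88%.
- Enrolled numbers, one-sided 5%: 93%.

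None reaches 99%. With 42 vs 27 and the two-sided t test, 99% power needs about 0.147 per year for PiB or 80.5 pg/mL per year for CSF.

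**The case against.** The best defence is that the term projected is never defined. Tables 8 and 9 label the column as a detectable effect, and the synopsis says calculated. Two-thirds of the reported effect is also smaller than the reported effect and could be called conservative, and both Sections 4.2.2 go on to give over 99% for exactly that quantity. On that reading the claim and the tables agree. For solanezumab this cannot be excluded, because no sentence calls 52.588 planned or projected. For gantenerumab it does not remove the conflict, because footnote 1 names 0.096 as the planned reduction.

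The second defence is titration. All gantenerumab subjects up-titrate after Amendment 5 with 1200 mg as the target, and Table 10 gives over 99% for the planned differences at 900 and 1200 mg. This stands and limits the point: a reader might infer that the true power of the biomarker comparison is simply 80%, and the documents do not support that. But Table 10 does not restore the unqualified sentence. Its effects are 0.096 multiplied by a dose ratio under an assumed linear relation, they presume 12 months on the stable dose, and Appendix 3 says that the target dose may not be reached.

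A reader might also infer that the interim would miss real target engagement one time in five. That does not follow. The interim is placed at 2 years, while 42 and 27 are 4-year completers; 5% annual attrition over 2 years leaves about 47 and 31 (52 × 0.95² and 34 × 0.95²), and power at 0.096 is then about 85%. The stopping criteria are left to the DSMB charter or SAP appendix, so nothing here shows that the gate is a 5% test.

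Lastly, by the protocol's own dates (last randomization December 2015) the 2-year interim fell due around December 2017, and this version cites data to May 2019. That lowers the urgency but does not make the sentences correct.

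**Conclusion.** Wrong as written. At the planning value that the protocol names for 225 and 450 mg, 0.096 per year, power is 80% and not over 99%. At 52.588 pg/mL per year it is also 80%; that this is the projected solanezumab effect is an inference from parallel wording. The over 99% holds for the reported effects, for two-thirds of them, and for Table 10's planned differences at 900 and 1200 mg; at 675 mg the figure is 98.7%.

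This rests on an assumed two-sided 5% t test, which recovers 52.588 exactly and 98.7% to the printed digit. The tabulated figures are sound; the fault lies in which effect the summary sentences attach the power to. No sample size and no claim on the primary cognitive endpoint depends on it. Whether the interim compares with direct or pooled placebos is a separate matter that may be settled in the SAP.

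**What to change.** In the synopsis and in Section 4.2.1 of Appendices 3 and 4, name the effect beside each power figure:
- 80% power at 0.096 per year for PiB C-SUVR (the 225/450 mg planning value) and at 52.588 pg/mL per year for total CSF Aβ42.
- Over 99% for two-thirds of the reported effects (0.333 and 113.3).
- For 675, 900 and 1200 mg, a reference to Table 10, noting that its figures rest on linear dose scaling of 0.096 and on 12 months at the stable dose.

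State the alpha and sidedness used. If the sponsor means some value other than 52.588 by the projected solanezumab effect, give that value and its power.

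The cost is wording only. No sample size, procedure or analysis changes, but the headline power becomes less favourable.
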